In an effort towards significantly reducing the intergenerational transmission of a wide range of mental disorders by intervening on parenting practices and clinically significant emotional dysregulation in parents and their preschool aged children, this proposal is to pilot test an integrated mental health and parenting intervention delivered via telehealth for 12 emotionally dysregulated parents with a history of substance use, in order to complete several foundational steps prior to conducting a larger scale randomized controlled trial. The proposed 20-week group therapy will integrate two evidence-based interventions: 1) Dialectical Behavior Therapy (DBT) Skills - targeting parental emotion dysregulation and substance use, and 2) Parent Training (PT) - targeting parenting behaviors linked to children's mental health. The telehealth format will enhance the scalability of the intervention and reduce many of the common barriers to access that parents face when seeking treatment for themselves or their children. The Specific Aims are to:

1. Determine feasibility, acceptability and implementation . Feasibility of recruitment (number of participants meeting eligibility on the initial online screener and number meeting eligibility following intake), feasibility of measurement tools (time taken to complete online questionnaires, missing data from questionnaires) and feasibility of the intervention (number of sessions attended by parents) will all be assessed to determine overall feasibility of the intervention study. Acceptability will be evaluated using measures of client satisfaction and a qualitative exit interview with each parent post-intervention. Implementation will be assessed by examining the frequency with which clients use DBT and parenting skills and by tracking clients' weekly skills use via a diary card.

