- P. The Coping with Children's Negative Emotions Scale (CCNES; Fabes, Eisenberg & Bernzweig, 1990) assesses parental self-report of emotion socialization practices. Parents are presented with 12 vignettes describing scenarios in which their children exhibit distress. Parents rate (on a Likert scale of 1-7) the likelihood they would engage in 6 potential parental responses to these situations, with each corresponding to 6 subscales: distress reactions, punitive reactions, minimization, expressive encouragement, emotion-focused reactions and problem-focused reactions. The first three can then be summed into an Invalidating/Unsupportive composite and the latter three can be summed into a Validating/Supportive composite.

- Q. Skill Use Diary Card. A diary card developed for this study will be used to assess parents' weekly use of specific DBT and parenting skills, both as a study measure of treatment dosage and for treatment purposes. Parents are asked to circle days of the week in which they used each skill. Additionally, they are asked if DBT Skills were used in a parenting or a non-parenting context. Diary cards also include an additional question that assesses for suicidal thoughts over the past week.
- R. The Client Satisfaction Questionnaire (CSQ-8; Attkisson & Zwick, 1982) will be used to assess acceptability of the intervention. It is a brief 8-item self-report measure in which clients are asked to rate (on a Likert scale of 1-4) their satisfaction with the intervention.
- S. Qualitative Exit Interview. A semi-structured exit interview will be used to evaluate parents' satisfaction with the intervention, challenges they experienced completing the intervention, their use of DBT/Parent training skills, and suggestions they have for improving the intervention delivery. Interviews will be video recorded so that representative quotes and themes can be identified.

Analyses

We will conduct multiple analyses to evaluate how, when, why, and to what extent the DBT Skills +PT intervention was effective in changing parents' mental health and/or parents' parenting quality and/or children's mental health and behavior. All data will be de-identified and all findings from our analyses will be reported anonymously.

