Aim 1. Determine feasibility, acceptability and implementation. Three types of feasibility will be examined. Feasibility of recruitment will be assessed by examining the number of participants meeting eligibility on the initial online screener and the number of participants meeting eligibility following the clinical intake. Feasibility of measurement tools will be assessed by calculating the average time taken by participants to complete the online Qualtrics questionnaires, and the average percentage of missing data from the online questionnaires. Feasibility of the intervention will be evaluated by calculating the average number of sessions attended by parents.

Acceptability will be examined by averaging the total scores obtained from the Client Satisfaction Questionnaire (CSQ-8). In addition, using qualitative thematic analyses, we will report on data collected during the exit interview, identifying overall themes about the intervention that emerge from parents' comments.

We will examine implementation by calculating the average daily number of DBT and parenting skills parents report using each week on their diary card (averaged across parents) and comparing these to skill use reported in other published research (ex. 7-8 DBT skills per week; Gamache [name] et al., 2017). We will primarily report data for Aim 1 at an aggregated group level. We may also include de-identified information at the individual level in the form of quotes from parents' exit interviews.

Aim 2. Evaluate pre-post and weekly changes. We will examine pre-post changes for the primary outcomes of DBT Skill use (DBT-WCCL), parental emotion dysregulation (DERS), parenting stress (PSI) and parenting quality (PS, CCNES). Pre-post change scores will also be calculated for the secondary outcomes of child internalizing and externalizing behaviors (CBCL), child emotion regulation (ERC), parent mental health symptoms (HAM-A, PHQ-9, ADCS). Pre-post change scores will be compared to the clinical trial literature base for DBT and parent training interventions which often use the same measures and for which expected change scores are established. Additionally, based on post-intervention reports during the SCID 5 diagnostic interview, the percentage of parents reporting sustained recovery (vs relapse) from substance use disorder will be calculated and reported.

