We will examine change across time based on data available in the weekly assessment measures of parents' DBT and parenting skill use (DBT-WCCL, Skill Use Diary Card), parents' emotion dysregulation (DERS), parenting quality (PS), and children's symptoms and behaviors (ERC and WACB). Consistent with common practice in case study designs (Kazdin, 2003; Kazdin, 2019; Rizvi & Nock, 2008), we will primarily use visual inspection (i.e. evaluating graphical displays of participants' weekly scores) to examine the data collected during Weeks 1-20 of the DBT Skills +PT intervention. We will use the same procedures to examine changes in data collected at the four time points representing the start of each DBT module. We will inspect several aspects of these data, such as changes in the trajectories of each measure, to determine the direction and extent of change in the measured symptoms and behaviors from week to week, and the timing of when those changes occurred. We will also characterize the order in which changes unfold over time (e.g. increased DBT skill use precedes improvement in parent emotion regulation, which precedes improvements in parenting quality measures, which precedes improvements in child behavior measures). These visual inspection analyses will be conducted at both the individual level and at an aggregated group level.

We will employ a number of standard methods of statistical analysis of single-case experimental design (SCED) data to further examine, quantify and corroborate results of visual inspection. Consistent with previous SCED studies, we will calculate Tau-U effect sizes (Parker et al., 2011; Vannest & Ninci, 2015; Brossart et al., 2018), linear regressions (Ramaiya et al., 2018) and perform hierarchical linear modeling which can be used to aggregate single-case results (Van den Noortgate & Onghena, 2007; Ugille et al., 2012). These analyses will provide preliminary information on the rate and order of change for the different targeted symptoms and behaviors, and enable us to report on the degree to which DBT Skills +PT changed parent-reported symptoms and behaviors at the level of individual parents as well as at the group level, aggregating data across all participating parents.

D. Research Population & Recruitment Methods

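### Aim 1 implementation sets a per-day skill count against a per-week, DBT-only example benchmark, and the text gives no conversion

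*Combined protocol and SAP*

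**What the plan says.** The Analyses text for Aim 1 (section C) assesses implementation by "calculating the average daily number of DBT and parenting skills parents report using each week on their diary card", averaged over parents. The sentence goes on to the comparison: "comparing these to skill use reported in other published research (ex. 7-8 DBT skills per week", followed by one citation. No other figure is offered for implementation.

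The raw data are described under Materials, item Q (Skill Use Diary Card): "Parents are asked to circle days of the week in which they used each skill". The card is meant to capture parents' "weekly use of specific DBT and parenting skills, both as a study measure of treatment dosage and for treatment purposes". It also collects context: "Additionally, they are asked if DBT Skills were used in a parenting or a non-parenting context".

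The aims in section B are worded more generally: "Implementation will be assessed by examining the frequency with which clients use DBT and parenting skills". That sentence then adds that skills use will be tracked weekly on the diary card. Both the aims and the description of the card therefore speak of weekly use, while the analysis sentence specifies a daily average.

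Aim 2 in the Analyses text separately follows "DBT and parenting skill use (DBT-WCCL, Skill Use Diary Card") across the treatment weeks.

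**The concern.** One sentence defines a quantity per day and compares it with a quantity per week. The words that place the daily average in each week say when it is calculated; they do not turn it into a weekly count. The benchmark also covers DBT skills alone, whereas the statistic names DBT and parenting skills.

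Implementation is one of the three parts of Aim 1, in a pilot meant to prepare for a larger randomized trial, and 7-8 per week is the only yardstick given for it. If the two figures are set side by side as written, the reader cannot tell whether parents used skills more or less than in the published work. If the benchmark counts skill-days, a group exactly at the benchmark would appear about seven times too low. If it counts distinct skills, the direction of the comparison can depend on how many days each skill was used, which a daily mean does not show.

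**Working it through.** **Inputs from the documents**
- Statistic: mean number of skills per day, calculated for each week (section C, Analyses, Aim 1).
- Benchmark: 7-8 DBT skills per week (same sentence). It is a literature value, and the documents hold nothing from which to reproduce it.
- Raw data: for each skill, the days of the week on which it was used (section C, Materials, item Q).

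**Assumptions**
- The study's own statistic is the number of circled skill-days in the week divided by 7. This is the natural reading of the card and the analysis sentence together.
- The cited study's counting rule is unknown here, so both possible rules are worked through.
- The card lists at least 8 DBT skills; otherwise 8 distinct skills could not be reached.

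**Rule 1: the benchmark counts skill-days.**
Daily equivalent = weekly count / 7.
7 / 7 = 1.00 and 8 / 7 = 1.14 per day. The factor is always 7, so multiplying the daily mean by 7 restores the match.

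**Rule 2: the benchmark counts distinct skills used at least once in the week.**
If B distinct skills are each used on d days, the daily mean is B × d / 7.

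| Days each skill is used (d) | B = 7 | B = 8 |
|---|---|---|
| 1 | 1.00 | 1.14 |
| 3 | 3.00 | 3.43 |
| 5 | 5.00 | 5.71 |
| 7 | 7.00 | 8.00 |

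The same benchmark maps to any value from 1.0 to 8.0 per day. The ratio of the weekly figure to the daily one is 7 / d, which runs from 7 down to 1, so there is no single multiplier.

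**Reverse check under Rule 2.** With S skill-days in one parent-week, the number of distinct skills lies between S / 7 rounded up and S.
- S = 7 (1.00 per day): 1 to 7 distinct skills.
- S = 8 (8 / 7 = 1.14 per day): 2 to 8 distinct skills.
- S = 21 (21 / 7 = 3.00 per day): 3 to 21 distinct skills, if the card lists that many.

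A parent at 3 skills per day could thus be well below or well above 7-8 distinct skills. The daily mean alone cannot say which.

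**DBT against DBT plus parenting.** The documents do not say how many parenting skills the card lists or how often they are used, so no size can be put on this difference.

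**The case against.** The best reply is that this is loose wording with little consequence. The figure is marked as an example. There is no threshold, progression rule or test attached to it. The target is 12 parents in a pilot. Day-level marks for each skill are kept, so any count can be derived later, and nothing forbids an analyst from rescaling to a week. The cited figure may even have been built in the same way as the planned statistic, with the weekly label as shorthand. The diary card itself (Appendix T) is listed but not in the supplied text, and could carry scoring detail. All of this stands, and it is why the point is minor. It does not remove a comparison that is stated in two different time units in one sentence.

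A reader might also infer more than the documents support:
- *That the plan gives no weekly framing.* It does: the aims and the description of the card both refer to weekly skills use. Only the analysis sentence departs from it.
- *That the study's own count is undefined.* The daily statistic is reasonably read as circled skill-days over 7. The open rule is mainly the cited study's.
- *That DBT and parenting skills will be pooled against a DBT-only figure.* The wording permits this but does not require it, and the effect cannot be calculated.
- *That the result will be wrong by a factor of seven.* This follows only if the benchmark counts skill-days and the two raw figures are placed side by side without rescaling.

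**Conclusion.** The point holds as a minor error in the plan as written: the implementation statistic is per day, while its only example benchmark is per week and DBT-only, with no conversion in the supplied text. The size depends on a rule that the documents do not give. It is a fixed factor of 7 (1.00-1.14 per day) if the benchmark counts skill-days, and a non-convertible range of 1.0-8.0 per day if it counts distinct skills. Confidence is high on the mismatch of units; the documents cannot settle which counting rule applies. The effect is confined to the interpretation of a descriptive Aim 1 result. Sample size, error rates and the Aim 2 examination of skill use over time are untouched.

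**What to change.** In the Aim 1 analysis text, define a separate figure for the comparison with published research:
- Compute from the diary card a weekly, DBT-only count in the unit that the cited study used. This is either the number of distinct DBT skills with at least one circled day in the week, or the weekly sum of circled DBT skill-days. If the cited study's unit is unclear, report both.
- Average over weeks within each parent, then across parents.
- Report parenting skills separately, and not against the DBT benchmark.
- Keep the daily average as a descriptive summary, not set beside the weekly figure.

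The cost is one or two sentences and a check of the cited study's definition. No new data are needed, because the card already records the days on which each skill was used. Fixing the rule before the data are examined also avoids choosing between the two counts after seeing the results.

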2. Evaluate pre -post and weekly changes in measures of parental emotion regulation, parenting **stress, parenting quality and children's mental health**. Across all parents enrolled in DBT+PT, we will evaluate the rate and pattern of change in these interlinked domains which represent risk factors for relapse and further adverse outcomes. We anticipate pre-post changes (2 time points, approximately 20-22 weeks apart) will be comparable to well-established change scores from the clinical trial literature base for DBT Skills and parent training interventions. Additionally, qualitative data from exit interviews with each parent will be analyzed using thematic analyses of responses to evaluate parents' perceptions of changes in their own mental health, their parenting and their children's behavior over the course of the intervention.

Weekly repeated measures (20 time points) will allow us to model the rate and pattern of change from week to week. As the intervention is divided into 4 modules (see Procedures), change patterns will also be examined between modules. Data will be presented descriptively and we expect changes to unfold in a cascading order, with increased use of skills preceding reductions in parent emotion dysregulation, followed by improvements in parenting quality and subsequent improvements in child behavior.

C. Methods, Materials and Analysis

Setting. Clinical intakes, the weekly group DBT Skills+PT intervention sessions, and exit interviews will all be conducted via a HIPAA compliant teleconference platform (i.e. Zoom). The initial online screener, and pre-post and weekly assessments will be conducted via UO Qualtrics questionnaires.

Study design. This study utilizes a mixed methods case study design with continuous assessment of quantitative measures. Figure 1 presents the study phases, along with what participating parents will complete in each phase, and the estimated time needed to complete each phase.

	time required of participants.	Time Estimate
Study Phase Recruitment	Participant action Parents respond to recruitment	N/A
Reciditment	materials	
↓		
Initial Online Screener	Parent completes:	
	DERS	DERS – 5 minutes
	CAGE-AID	CAGE-AID – 2 minutes
		Total: 7 minutes
•		
Clinical Intake	Parent completes:	Demographica 4 minutes
_	Demographic questionnaire	Demographics – 4 minutes
	PHQ-9	PHQ-9 - 3 minutes
	PPVT-V (Q-Global) SCID 5 diagnostic interview	PPVT-V – 20 minutes SCID 5– 180-300 minutes
		Total: 207-327 minutes
.		

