Following this, parents will complete a demographic questionnaire, the Peabody Picture Vocabulary Test-V (PPVT-V Q-Global), the Patient Health Questionnaire for Depression (9-items; PHQ-9), and the Structured Clinical Interview for DSM-5 (SCID 5). Parents will be ineligible to participate if they meet for the exclusionary criteria detailed in section D. Research Population & Recruitment Methods: Participants.

Pre-intervention Assessment. Parents who meet criteria for the study following the clinical intake will be asked to complete a broad battery of questionnaires (see Fig 1. Study Phase: *"Pre-intervention"*) to assess parent mental health symptoms, parenting stress, parenting quality and child mental health symptoms. The questionnaires will be completed online via UO Qualtrics and parents will receive an encrypted email (i.e. Hushmail) from the project coordinator with the UO Qualtrics link.

DBT Skills +PT intervention. The study plans to recruit three groups of approximately 4-5 parents/group. Parents will be recruited twice throughout the course of the year to facilitate running up to three groups (see section D. Research Population & Recruitment Methods for more details). Once a group of parents has been recruited, participants will take part in 20 weekly DBT Skills +PT intervention sessions. The group sessions are conducted remotely over a HIPAA compliant version of Zoom and groups are led by [name] (PI) and three other doctoral level student co-leaders who are supervised by [name], a licensed clinical psychologist who is trained in both DBT and parent training. [name] [name] (Co-I) and [name] (Faculty Advisor) may also be consulted and provide supervision, when needed.

Prior to the start of the first session, co-leaders will conduct 1 hour individual orientation sessions over Zoom with each participating parent, in order to orient them to the intervention, review intervention related portions of the consent form, and provide participating parents with an opportunity to ask questions in private if they wish.

Before each weekly session, parents will receive an encrypted email from the project coordinator asking them to complete the 5 measures listed in Fig. 1: Study Phase: "Treatment Phase", via a set of online UO Qualtrics questionnaires.

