A single informed consent form (see Appendix A. Informed Consent Form) will cover all phases of the study (clinical intake, pre-intervention assessment, intervention, and post-intervention assessment). Prior to the clinical intake, a copy of the Informed Consent Form will be emailed to participants. At the start of the clinical intake, a trained research staff member will give each parent an overview of the study in its entirety and review confidentiality practices, potential risks, and any benefits. Participants will also be informed that as this is an intervention development project, the intervention group coleaders are involved in the research and will have access to assessment data. Limits to confidentiality will be covered (as in the case of abuse of vulnerable populations, harm to self or others), as will the steps that will be taken if this information is revealed. Because the clinical intake and the assessments will specifically ask about suicidality, parents will be told in detail what procedures will occur if they are judged to be a risk to themselves or others (see Appendix X. Critical Risk Protocol). Parents will be invited to ask questions and will then provide consent via electronic signature on the Informed Consent Form and email it back to the staff member conducting the clinical intake.

At the start of the post-intervention qualitative interview, the trained research staff member conducting the interview will briefly cover the purpose of the exit interview and review the relevant portion of the consent form with the parent. Parents will be asked to verbally reaffirm their consent to participate. We will clearly track that the parent's consent to participate in the study was collected at the clinical intake and at the post-intervention exit interview (see Appendix Z. Documentation of Informed Consent).

A copy of the informed consent form will be posted on a Federal website (e.g. clinicaltrials.gov) after the study is closed to recruitment and no later than 60 days after the last study visit by any subject.

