Roles and Research Duties. The principal investigator ([name]) and faculty advisor ([name]) will be involved in all aspects of this research. The co-Investigator ([name]) will help in the development and refinement of intervention session plans and will be highly involved in preparing resultant manuscripts from this study. The clinical supervisor ([name]) will provide supervision for all intervention coleaders by reviewing video recordings of sessions and meeting with co-leaders regularly to provide clinical feedback. The project coordinator will be involved in the development of recruitment materials, recruitment efforts, scheduling, data collection, data storage and following of procedures for this protocol. [name] (PI) will train all research assistants who may be involved in qualitative coding of the exit interviews. In addition, [name] and the additional co-leaders will be responsible for conducting clinical intakes and co-leading the DBT+PT intervention. A trained clinical psychology graduate student will be responsible for conducting the exit interviews.

Training and Oversight. [name] (PI), the other group co-leaders and [name], will participate in weekly consultation meetings. These consultation team meetings are designed to assist co-leaders in adhering to the DBT treatment model and the Parent Training manual. All research personnel involved in recruitment, screening, intakes, assessments and the intervention will complete the Collaborative Institutional Training Initiative's (CITI) Protection of Human Research Subjects program for Social-Behavioral-Educational Researchers as well as the Good Clinical Practices training to ensure ethical and professional conduct of the research. Study personnel will complete and have up-to-date CITI training certificates on file with the Project Coordinator. Additionally, each member of the study team will be trained by the PI to follow the approved research protocol.

Appendices submitted with this application

- A. Informed Consent Form
- B. Recruitment Email
- C. Craigslist Posting
- D. Facebook Posting
- E. Online Screening Script
- F. Intake Scheduling Script
- G. Difficulties with Emotion Regulation Scale (DERS)
- H. CAGE-AID Screener
- I. Demographic Questionnaire
- J. Patient Health Questionnaire 9 (PHQ-9)
- K. Hamilton Anxiety Rating Scale (HAM-A)
- L. The Aggregated Drug Craving Scale (ADCS)
- M. DBT Ways of Coping Checklist (DBT-WCCL)

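### The primary reading of the weekly graphs, which dates each change and its order, has no masking, no onset rule and no single score per domain, while treatment staff have access to the data

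*Combined protocol and SAP*

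**What the plan says.** Section C (Analyses, Aim 2) states that "we will primarily use visual inspection (i.e. evaluating graphical displays of participants' weekly scores) to examine the data collected during Weeks 1-20". The inspection covers direction, extent and timing of change, and "These visual inspection analyses will be conducted at both the individual level and at an aggregated group level". The same text then says: "We will also characterize the order in which changes unfold over time (e.g. increased DBT skill use precedes improvement in parent emotion regulation". Section B (Aim 2) gives the prediction: "we expect changes to unfold in a cascading order, with increased use of skills preceding reductions in parent emotion dysregulation", followed by parenting quality and then child behavior.

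The weekly measures named for this analysis are DBT-WCCL and the diary card (skill use), DERS (parent dysregulation), PS (parenting quality), and ERC and WACB (child). Two of the four domains therefore have two instruments each.

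On who is involved:
- Section C (Procedures): "groups are led by [name] (PI) and three other doctoral level student co-leaders".
- Section I (Roles and Research Duties): the principal investigator and faculty advisor "will be involved in all aspects of this research".
- Section E: participants are told that "the intervention group coleaders are involved in the research and will have access to assessment data".
- Section C (Materials, item Q): the diary card serves "both as a study measure of treatment dosage and for treatment purposes".

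The exit interview is reserved for a staff member who did not co-lead groups (Section C, Post-intervention Assessment). The text available states no such separation for reading the graphs. It also gives no masking, second reader, agreement measure or definition of onset.

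**The concern.** Dating the start of a change by eye on a noisy 20-point series leaves room for judgement. A reader who knows which line is DERS and which is PS, and who expects DERS to move first, can resolve unclear turns in that direction without meaning to. Where a domain has two instruments, the reader can also take whichever fits. The team saw the value of keeping co-leaders out of the exit interview, but the method that is primary for the weekly data has no comparable protection.

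At stake is how far a reported cascade can be believed. The pilot is meant to complete groundwork before a larger randomised trial, and the order of change is one of the things Aim 2 sets out to describe. If the order is read with knowledge of the labels and free choice of measure, readers of the report cannot separate a pattern in the data from one supplied by expectation.

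**Working it through.** The plan gives no error rate or threshold for the visual reading, so there is no figure to reproduce. Two things can be checked: what the text provides, and how much freedom the choice of measure leaves.

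**Inputs.** Four ordered domains (Section B, Aim 2). Two skill measures, one dysregulation measure, one parenting measure and two child measures (Section C, Analyses, Aim 2). Target of 12 parents (Section D, Participants).

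**Assumptions, not in the documents.** No true order; onset weeks exchangeable and without ties; parents independent; every parent has an onset on every measure. The criterion of at least 2 of 12 parents is this review's own, because the plan sets none.

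**Step 1: one fixed measure per domain.** There are 4! = 24 equally likely orders, so the expected order appears with probability 1/24 = 4.2% per parent.

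**Step 2: free choice within the skill and child domains, paired measures independent.** The reader can take the earlier skill onset and the later child onset. With onsets scaled to be uniform on 0 to 1:

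P[min(S1,S2) < D < P < max(C1,C2)] = ∫₀¹ (1 − p²) [∫₀ᵖ (2d − d²) dd] dp = ∫₀¹ (1 − p²)(p² − p³/3) dp

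= 1/3 − 1/12 − 1/5 + 1/18 = (60 − 15 − 36 + 10)/180 = 19/180 = 10.6% per parent.

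**Step 3: at least 2 of 12 parents.** P = 1 − (1 − q)¹² − 12q(1 − q)¹¹.
- q = 1/24: 1 − 0.600 − 0.313 = 8.7%.
- q = 19/180: 1 − 0.262 − 0.371 = 36.6%.

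**Step 4: paired measures that move together.** Both measures in a pair come from the same parent's reports, so independence is the extreme case. The table repeats the calculation by simulation, with an assumed correlation between the onsets within each pair (normal scores, 3,000,000 draws per row).

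| Within-pair correlation | Per parent | At least 2 of 12 |
|---|---|---|
| 0 | 10.6% | 37% |
| 0.5 | 8.3% | 26% |
| 0.8 | 6.6% | 18.5% |
| 0.9 | 5.8% | 15% |
| 1.0 | 4.2% | 8.7% |

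The documents give no such correlation, so the range from 0 to 0.9 is the honest statement.

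**Step 5: a simple onset rule is not automatically safe.** Take onset as the first of three consecutive weeks above both the pre-intervention and the Week 1 score. In simulated series with noise and no change, this gives a false onset somewhere in Weeks 2 to 20 in about 40% of series at autocorrelation 0, 58% at 0.5 and 64% at 0.7 (autocorrelations assumed). It also cannot be applied to the diary card, which is absent from the pre-intervention battery in Figure 1.

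**Step 6: workload.** 12 × 6 = 72 parent graphs plus 6 group graphs = 78. At the maximum enrolment of 15, 90 + 6 = 96.

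**The case against.** The strongest reply is that the plan does not rest on eyesight alone. Section C assigns Tau-U, linear regression and hierarchical models to examine and quantify the results as well as corroborate them, and says that they will give preliminary information on rate and order of change. This stands, and it softens the point. It does not dispose of it: visual inspection stays primary, no model for dating onsets is specified, and nothing says what is reported if models and graphs disagree.

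Second, this is a descriptive pilot. Section B says that the weekly data will be presented descriptively, and the primary outcomes named for Aim 2 are pre-post changes. That also stands and limits the severity. A reader might infer that the cascade is the result on which the later randomised trial will be built; no passage says so.

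Third, a reader might infer that therapists will read the graphs and bend them towards the prediction. The documents do not support that as fact. They place the principal investigator in all aspects of the research and give co-leaders access to assessment data, but they name no reader. The risk follows from those roles together with the lack of safeguards.

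Fourth, announcing the order in advance might look like the fault. It is prespecification and should stay.

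Finally, masking the graphs does nothing about bias in the parents' own reports. This is true, and it is a limit of the remedy.

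**Conclusion.** The point holds in a limited form. The primary method for dating and ordering weekly change is a judgement made without masking, onset rule or fixed score per domain, in a team that includes those who deliver the treatment and have access to the data.

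Under no true order and exchangeable onsets, free choice of instrument in two domains moves the chance of at least 2 of 12 apparent cascades from 8.7% to somewhere between about 15% and 37%. It would be tempting to read the upper figure as the size of expectation bias, or as what masking would remove. It is neither. It measures choice of instrument only, the upper end needs paired measures to be independent, and naming one measure per domain removes the whole increase without any masking. The benefit of masking is plausible but not quantified. Parents with few weekly reports may also contribute no order at all, since the target counts anyone who completes at least 4 sessions.

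For a descriptive pilot of 12 parents, this is a change worth considering rather than one the study cannot do without.

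**What to change.** Before any graph is inspected:

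1. Name one score per domain for the order result, for example the DBT-WCCL skills score, DERS total, PS total and one named WACB or ERC score. Naming the instrument alone is not enough for the child domain, because WACB has two scales and ERC has two subscales and a composite. Show all other measures as supportive.
2. Write one onset rule, with a category for no change. Check by simulation how often it declares an onset in a series without change. The three-weeks rule in step 5 of the working should not be used.
3. Have the project coordinator, who already handles data storage, produce graphs with coded measure and parent labels, rescaled and oriented so that up means improvement. Lock the recorded onset weeks before unmasking.
4. Where possible, use existing staff who did not lead groups as readers, such as the exit interviewer or the research assistants trained for qualitative coding. Co-leaders may recognise a parent's course from the diary cards.
5. State what will be reported if the models and the graphs disagree on order.

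Cost: a plotting script for 78 to 96 graphs and a few hours of existing staff time, with no new data and no added burden on parents. Masking will be imperfect where a measure has a recognisable pattern, and bias in the parents' own reports remains.
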